6. Infant is not naive to a weighted wearable blanket.

Study Design

Direct observational pilot study of the safety of weighted wearable blankets on a minimum of (10) healthy infants aged 0-12 months with nap polysomnogram. Participants will be placed in a weighted wearable blanket, in accordance with their age/weight/height, by their parent or caregiver under the supervision of a member of the study team. After being put to sleep on their back, the participant will remain in the weighted wearable blanket until completion of the nap polysomnogram.

Enrollment/Recruitment

The target number of total participants is a minimum of 10 infants. The recruitment strategy aims to achieve representation of minority groups that reflects the demographics of the population in the catchment area. At least 5 infants must be 0-3 months and all others can be any age between 0 and 12 months of age.

Participants will be recruited in a variety of ways:

Flyers will be posted in the hospital(s) and/or on campus in places frequented by potential participants (e.g., elevators, food courts, parking garage elevators) or public places such as parks, grocery stores or churches. In addition, we will provide flyers and/or brochures to the various maternity wards at Riley, University & Methodist.

Brochures will be available for patients referred to the Sleep Center at Riley or established patients at a clinic visit. Patients who are already scheduled for a sleep study, and meet eligibility criteria, will be contacted by phone and introduced to the study. If the patient is interested, we will send the brochure and the consent (either by USPS or email).

The flyers and brochures will be shared with faculty physicians (in the division of Pediatric Pulmonology, Allergy and Sleep Medicine) as well as RN and other staff in the Sleep Center and maternity wards (for informational purposes only, they will not consent subjects). We might also include the flyer in weekly newsletters and/or internal communications.

Social media ads will be placed on Facebook and/or Instagram and clicking on this ad will direct potential participants to the study's web site

(<https://dreamlandbabyco.com/pages/clinical-trial>) where they can find phone and email information for the study team.

Study Procedures

During this study, participants will have one study visit. This visit will take place in the Sleep Center at Riley Hospital for Children at IU Health.

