- Informed consent – we will explain the study and ask for written consent; participants will receive a signed copy of the consent to keep
 - depending on how the participant was recruited, the informed consent discussion and written consent may have already occurred virtually
- Review of inclusion/exclusion criteria
- Collection of demographic data (infant age, sex, weight) and review of clinical data (current medications, other non-pharmacologic interventions, evidence of cardiac, neurological, or pulmonary disorders) from participant medical records and parent report
- Vital signs measurements (heart rate, respiratory rate, body temperature, oxygen saturation) will be obtained at baseline and monitored throughout the sleep study
- Height and weight measurements will be obtained once, at baseline
- Participants will be placed in weighted wearable blanket such that the blanket does not cover the head/face or restrain the infant
- Participants will then be put to sleep on their backs
- Vital signs will be monitored over a 6–8-hour period with standard polysomnography equipment
- Upon infant awakening at the end of the nap, the weighted wearable blanket will be removed, and vital sign measurements will be repeated
- One week after the nap polysomnogram, subjects will be contacted by phone to complete a short questionnaire

The following stopping parameters will be used for this study. Parameters are noted when the infant is quietly sleeping and the changes observed are not due to agitation or crying. Baseline data will be recorded before and after placing the infant into the weighted, wearable blanket.

Endpoint	Stopping Parameters
Heart rate	Persistent increase by >20 from baseline for 15 minutes
Respiratory rate	Persistent increase by >10 from baseline for 15 minutes
Body temperature	Increase by more than 2° from baseline
Oxygen saturation	Persistent drop by >10% from baseline
Infant movement	Agitation and unable to settle to sleep >15 minutes

If any of the stopping parameters are met, the weighted blanket will be opened to assess if the weighted blanket is responsible for the change. If determined yes, the weighted blanket will be removed and the nap polysomnogram will be terminated.

Reportable Events

We will follow the IU HRPP Reportable Events Policy and Guidance, as needed. Severe adverse events (SAEs) will be reported to the FDA in accordance with 21 CFR 312.32.

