An adverse event (AE) is defined as any untoward medical occurrence associated with the use of a drug or device in humans, whether or not considered drug- or device-related. An SAE is defined as an adverse event or suspected adverse reaction is considered "serious" if, in the view of the investigator, it results in any of the following outcomes: Death, a life-threatening adverse event, inpatient hospitalization or prolongation of existing hospitalization, a persistent or significant incapacity or substantial disruption of the ability to conduct normal life functions, or a congenital anomaly/birth defect. Important medical events that may not result in death, be life-threatening, or require hospitalization may be considered serious when, based upon appropriate medical judgment, they may jeopardize the patient or participant and may require medical or surgical intervention to prevent one of the outcomes listed in this definition. Collection of AEs and SAEs will begin at the time of consent.

Loss of confidentiality is always a potential adverse event and will be reported per existing Indiana University and Indiana University Health policies.

Study Withdrawal/Discontinuation

Participants are free to withdraw from participation in the study at any time for any reason.

The study team may discontinue a participant from the study for any of the following reasons:

- Unacceptable adverse event(s)
- Significant study intervention non-compliance
- The participant meets an exclusion criterion (either newly developed or not previously recognized) that precludes further study participation

Statistical Considerations

Sample Size Considerations

In the pilot safety study, the total sample size will be a minimum of 10 infants. All participants will receive the same intervention. Data from all participants who complete both baseline and follow-up assessments will be included in the analysis.

Statistical Analysis Plans:

Primary Analysis (Safety)

Means and standard deviations for each vital sign will be calculated at both baseline and during the intervention. Summary statistics based on demographic and baseline characteristics will be gathered. A Paired t-test will be performed to compare the means

of each vital sign at baseline and during the intervention. We will also use a linear mixed effect model to determine differences in vital signs.

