The t-statistic and corresponding p-value will be calculated at a significance level of 0.05 alpha. If the p-value is less than 0.05, this will be interpreted as a statistically significant difference in the vital sign before and after wearing the weighted wearable blanket. If the p-value is greater than 0.05, this will be interpreted as no significant difference in the vital sign before and after wearing the weighted wearable blanket.

Reporting and Documentation of Results

Measures and Instruments

Polysomnography (PSG) Equipment

PSG will be conducted using a multi-channel PSG system Respiration Alice G3 that is designed for sleep studies. The system will include the following components: Electroencephalography (EEG) to measure brain activity, Electromyography (EMG) to monitor muscle activity, Electrooculography (EOG) to record eye movements, Electrocardiography (ECG) for heart rate monitoring, Respiratory effort belts to measure chest and abdominal movements, Nasal and oral airflow sensors to monitor airflow, Pulse oximetry to measure oxygen saturation levels, and Video recording for behavioral monitoring during sleep. Prior to each PSG recording, the equipment will be calibrated according to American Academy of Sleep Medicine (AASM) guidelines to ensure accurate measurements, and quality control checks will be performed regularly to ensure proper functioning of sensors and electrodes during the study. The following physiological variables will be continuously measured and recorded during PSG:

- Electroencephalography (EEG): EEG electrodes will be placed according to the international 10-20 system to record brain activity and identify sleep stages (e.g., wake, NREM, REM).
- Electromyography (EMG): EMG electrodes will be positioned to monitor muscle activity, including chin and limb muscles, to assess muscle tone and movements during sleep.
- Electrooculography (EOG): EOG electrodes will be used to detect eye movements, which are important for distinguishing sleep stages and identifying rapid eye movement (REM) sleep.
- Electrocardiography (ECG): ECG electrodes will be placed to monitor heart rate and detect any cardiac abnormalities during sleep.
- Respiratory Parameters: Respiratory effort belts will record chest and abdominal movements to assess breathing patterns; Nasal and oral airflow sensors will measure airflow and detect apnea and hypopnea events; and Pulse oximetry will monitor oxygen saturation levels.

Privacy/Confidentiality

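### The primary safety analysis compares only means, so brief oxygen or breathing events in a few infants would not show in it, and the events the polysomnogram can detect are neither endpoints nor analysed

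*Combined protocol and SAP*

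**What the plan says.** The endpoint table (Outcome Measures/Endpoints) lists heart rate, respiratory rate, body temperature, oxygen saturation and observed movement. Under Primary Analysis (Safety) the plan is: "Means and standard deviations for each vital sign will be calculated at both baseline and during the intervention". A paired t-test then compares the baseline mean with the mean during the intervention, and the section adds: "We will also use a linear mixed effect model to determine differences in vital signs". No terms, covariance structure or time unit are given for that model. On interpretation the plan says: "If the p-value is greater than 0.05, this will be interpreted as no significant difference in the vital sign".

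The recordings hold more than this. Study Procedures says: "Vital signs will be monitored over a 6–8-hour period with standard polysomnography equipment". Measures and Instruments says: "Nasal and oral airflow sensors will measure airflow and detect apnea and hypopnea events", and lists oximetry among the continuously recorded signals. No apnea, hypopnea or desaturation count, lowest saturation, or time at low saturation appears in the endpoint table or in any analysis.

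**The concern.** The Background describes the feared harm as compression of the chest that impairs breathing, and the pilot is meant to assess lowered respiration. Such harm could appear as a sustained shift in everyone, which a mean can detect. It could also appear as short or intermittent falls in a few infants, to which a mean is insensitive. Followed as written, the plan could report no significant difference in oxygen saturation while its own recordings showed clear desaturations in one to three infants. Readers of a safety pilot would take that as reassurance. The point concerns the continuously recorded signals, above all oxygen saturation. Ear temperature is taken as spot readings and is not part of it.

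**Working it through.** The sample size has no power or precision calculation behind it, so there is no planned figure to reproduce.

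**Inputs from the document.** n = 10, since "the total sample size will be a minimum of 10 infants" (Sample Size Considerations). Alpha is 0.05; sidedness is not stated and is taken as two-sided. Recording length is 6 to 8 hours (Study Procedures).

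**Assumptions, because the document gives no figures.** Depth and duration of a fall; the SD of within-infant change in mean saturation; and, for steps 2 and 3, that the mean covers the whole recording.

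**Step 1: how many infants must be affected.** Let k of n infants have an equal fall d and the others no change. The mean change is kd/n and the variance of the changes is d²k(n−k)/[n(n−1)]. So t = √[k(n−1)/(n−k)], and d cancels. For n = 10 this is t = 3√[k/(10−k)] on 9 df:

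| Infants with a fall | t | two-sided p |
|---|---|---|
| 1 | 1.00 | 0.343 |
| 2 | 1.50 | 0.168 |
| 3 | 1.96 | 0.081 |
| 4 | 2.45 | 0.037 |

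Unequal falls give a smaller t. This result holds for any averaging window. Ten is a minimum, but modest over-enrolment does not help: three affected infants give p of about 0.082–0.083 at n = 12, 15 or 20.

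**Step 2: dilution within one infant.** The shift in an infant's mean is depth × minutes / (hours × 60). For a 10-point fall:

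| Duration | 6 h recording | 8 h recording |
|---|---|---|
| 1 min | 10 × 1/360 = 0.028 | 10 × 1/480 = 0.021 |
| 5 min | 0.139 | 0.104 |
| 15 min | 0.417 | 0.313 |

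A shorter recording dilutes less: 5 minutes in 1 hour gives 10 × 5/60 = 0.83 points.

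**Step 3: adding noise.** The other infants will not show exactly zero change. With an assumed SD of 0.25–1.0 points, a 7-hour mean and 200,000 simulated trials, one infant with a 5-minute, 10-point fall gives p < 0.05 in the downward direction in 2.7–3.3% of trials. A 15-minute fall gives 3.0–4.3%. With no fall at all the figure is 2.5%. Noise can carry a larger effect over the line, but not often: with three infants whose whole-recording means drop by 2 or 5 points (SD 0.5–2), the test is significant in the downward direction in 9–19% of simulated trials.

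**Step 4: what a count of affected infants would offer.** The chance that at least one of 10 infants shows an event is 1 − (1−π)¹⁰, where π is the true proportion of infants with an event: 40% at π = 5%, 65% at 10% and 89% at 20%. If none does, the one-sided 95% upper bound is 1 − 0.05^(1/10) = 0.259.

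**The case against.** - **Events would be seen at the bedside.** A team member monitors throughout, there are stopping parameters, and adverse events are collected from consent. This stands, and the claim is limited to the planned analysis. The oxygen parameter is "Persistent drop by >10% from baseline", with no duration given, and the respiratory parameter refers only to a sustained increase. Neither these nor adverse events are assigned a planned summary.
- **The 15-minute example is near what the stopping parameter already covers.** Fair. The 1- and 5-minute rows carry the argument better.
- **The p-values in step 1 belong to the paired t-test alone.** Correct. The mixed model might behave differently. One illustrative random-intercept model (assumed 30-second epochs, 20 at baseline and 840 in the blanket, within-infant SD 1 point, 15 runs per case) gave p far below 0.001 for a 10-point fall lasting one infant's whole recording. It still missed falls of 5 and 15 minutes (median p about 0.6 and 0.5), so the insensitivity to brief events remains.
- **The comparison may use spot readings.** The interpretation text speaks of before and after wearing the blanket, and vital signs are repeated at the end. In that case dilution is not the mechanism, but brief events are still missed.
- **A pilot of 10 cannot establish safety.** True. That favours describing each infant over relying on a p-value.

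**Conclusion.** The point holds. The planned safety analysis can detect a sustained average shift but not short or intermittent respiratory events in a minority of infants, and the measures that would describe those events are absent from both endpoints and analysis. For the paired t-test at n = 10, falls confined to one, two or three infants give at best p = 0.34, 0.17 or 0.08 when the others do not change; four equal falls are needed for p < 0.05. That result needs no assumed SD, depth or window. The dilution figures (0.10–0.14 points for a 10-point, 5-minute fall) rest on a whole-recording mean and on illustrative depths and durations. The study can run as designed, but this should be corrected before the data are analysed, because leaving event measures unplanned also leaves the choice among them open once results are known.

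**What to change.** Add to the endpoint table and the primary safety analysis, for each infant:

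- lowest oxygen saturation;
- percent of sleep time below a saturation level fixed in advance;
- desaturations per hour of sleep;
- apneas plus hypopneas per hour of sleep, scored by the sleep laboratory's usual criteria.

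List these, with hours of sleep recorded, for every infant placed in the blanket, including any whose recording is stopped early. The present analysis set requires both baseline and follow-up assessments and does not say whether such an infant qualifies. Summarise by median and range. State the window over which means are taken, and keep the means as supporting summaries.

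State that the event results are descriptive. Because "the participant will remain in the weighted wearable blanket until completion of the nap polysomnogram", no blanket-off sleep is planned and events cannot be attributed to the blanket. With 0 of 10 infants affected, a true proportion of up to about 26% is still not excluded (one-sided 95%).

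The cost is endpoint and SAP wording, scoring time on recordings already planned, and a few more reported outcomes. No infant, visit or procedure is added, and the stopping parameters are untouched.
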